2.1.3 Informed Consent Process

Investigators must ensure that subjects are clearly and fully informed about the purpose, potential risks, and other critical issues regarding clinical studies in which they volunteer to participate.

In situations where consent cannot be given to subjects, their legally acceptable representatives (as per country guidelines) are clearly and fully informed about the purpose, potential risks, and other critical issues regarding clinical studies in which the subject volunteers to participate.

Sponsor or designee will provide the investigator with an appropriate (ie, Global or Local) sample informed consent form which will include all elements required by ICH, GCP and applicable regulatory requirements. The sample informed consent form will adhere to the ethical principles that have their origin in the Declaration of Helsinki.

Investigators must:

- 1) Provide a copy of the consent form and written information about the study in the language in which the subject is most proficient prior to clinical study participation. The language must be non-technical and easily understood.
- 2) Allow time necessary for subject or subject's legally acceptable representative to inquire about the details of the study.
- 3) Obtain an informed consent signed and personally dated by the subject or the subject's legally acceptable representative and by the person who conducted the informed consent discussion.
- 4) Obtain the IRB/IEC's written approval/favorable opinion of the written informed consent form and any other information to be provided to the subjects, prior to the beginning of the study, and after any revisions are completed for new information.
- 5) If informed consent is initially given by a subject's legally acceptable representative or legal guardian, and the subject subsequently becomes capable of making and communicating his or her informed consent during the study, consent must additionally be obtained from the subject.
- 6) Revise the informed consent whenever important new information becomes available that is relevant to the subject's consent. The investigator, or a person designated by the investigator, should fully inform the subject or the subject's legally acceptable representative or legal guardian, of all pertinent aspects of the study and of any new information relevant to the subject's willingness to continue participation in the study. This communication should be documented.

The confidentiality of records that could identify subjects must be protected, respecting the privacy and confidentiality rules applicable to regulatory requirements, the subjects' signed ICF and, in the US, the subjects' signed HIPAA Authorization.

The consent form must also include a statement that BMS and regulatory authorities have direct access to subject records.

Subjects unable to give their written consent (eg, stroke or subjects with or severe dementia) may only be enrolled in the study with the consent of a legally acceptable representative. The subject must also be informed about the nature of the study to the extent compatible with his or her understanding, and should this subject become capable, he or she should personally sign and date

the consent form as soon as possible. The explicit wish of a subject who is unable to give his or her written consent, but who is capable of forming an opinion and assessing information to refuse participation in, or to be withdrawn from, the clinical study at any time should be considered by the investigator.

The rights, safety, and well-being of the study participants are the most important considerations and should prevail over interests of science and society.

3 INVESTIGATIONAL PLAN

3.1 Study Design and Duration

Protocol CA209651 is a randomized open-label, Phase 3 trial in subjects ≥ 18 years old with untreated metastatic or recurrent SCCHN that is not amenable to curative therapy, evaluating nivolumab + ipilimumab versus the EXTREME regimen (cetuximab + cisplatin/carboplatin + fluorouracil) as a first-line treatment.

HPV p-16 status and tumor cell PD-L1 status (expressing or non-expressing/non-evaluable) test results will be needed prior to randomization. Subjects will undergo screening evaluations to determine eligibility prior to randomization.

The dose and treatment schedules for each arm are as follows:

- Arm A: Nivolumab + Ipilimumab Arm:
 - Nivolumab 3 mg/kg IV every 2 weeks + Ipilimumab 1 mg/kg IV every 6 weeks until progression, unacceptable toxicity, or a maximum of 24 months from first study treatment.
- Arm B: EXTREME regimen Arm:
 - Cetuximab 400 mg/m² IV for the initial dose only, then 250 mg/m² weekly + cisplatin (100 mg/m²) or carboplatin (AUC of 5 mg per milliliter per minute) on Day 1 and fluorouracil (1000 mg/m² per day for 4 days) every 3 weeks for maximum of 6 cycles followed by maintenance cetuximab at 250 mg/m² weekly (or every 2 weeks, per local prescribing information) until disease progression or unacceptable toxicity; the choice of cisplatin or carboplatin is at the discretion of the investigator.

Approximately 930 subjects will be randomized to the two treatment arms in a 1:1 ratio and stratified by the following factors:

- Tumor cell PD-L1 status (expressing [$\geq 1\%$] vs non-expressing [$< 1\%$] or non-evaluable). Up to 10% of randomized subjects per cohort can be included into the study as “non-evaluable.” After this point, subjects with non-evaluable results will not be permitted to be randomized; the site would need to submit an additional tumor tissue for testing with either a result of “expressing” or non-expressing” in order to randomize the subject.
- HPV p-16 status (oropharyngeal HPV p-16 positive vs oropharyngeal HPV p-16 negative or non-oropharyngeal). Oropharyngeal CA sites defined in [Appendix 5](#).
- Prior chemotherapy (adjuvant/neoadjuvant/multimodal treatment) status (Yes/No)

Tumor progression or response will be assessed by investigator using RECIST 1.1 criteria. Treatment with study medication will continue until RECIST 1.1 defined progression, unacceptable toxicity, a maximum of 24 months from the first study treatment, or withdrawal of consent. See [Section 3.5](#) for full details of discontinuation of study drug treatment.

Dose reductions will not be allowed for nivolumab or ipilimumab.

Treatment beyond initial investigator-assessed progression (either clinical or radiographical) is permitted for nivolumab and ipilimumab if the participant has an investigator-assessed clinical benefit and is tolerating study drug (see [Section 4.5.6](#)).

[figure not shown]
In addition to investigator assessment of response and progression, there will be a blinded independent central review (BICR) of tumor scans and study sites will need to submit tumor scans for central radiology review.

A DMC will be established and meet regularly during the study to ensure that participant safety is carefully monitored and to provide oversight regarding safety and efficacy considerations in protocol CA209651.

The maximum duration of the study from start of randomization to final analysis of OS is projected to be 51 months, assuming 26 months accrual duration. Additional survival follow-up may continue for up to 5 years from the time of this analysis. The study will end once survival follow-up has concluded.

The study design schematic is presented in Figure 3.1-1.

Figure 3.1-1: Study Design Schematic

This study will consist of 3 phases: screening, treatment, and follow-up.

Screening Phase

- Begins by establishing the participant's initial eligibility and signing of the informed consent (ICF).
- Participant is enrolled using the Interactive Voice Response System (IVRS).
- Tumor tissue (archival or recent tumor biopsy) must be submitted by the site to a Central Lab for determination of tumor cell PD-L1 status. For this study we will use PD-L1 stained with the DAKO 28-8 antibody. Additional tumor tissue may be required by Central Lab if initial testing is unevaluable.
- HPV p-16 status must be available prior to randomization. If it is not available locally, then this will need to be tested by central lab, and the results need to be known prior to randomization. See [Section 5.6.8](#).

Participants will be stratified on tumor cell PD-L1 status (expressing vs non-expressing or non-evaluable. Up to 10% of randomized subjects can be included into the study as non-evaluable. After this point, subjects with non-evaluable results will not be permitted to be randomized; the site would need to submit an additional tumor tissue for testing with either a result of expressing or non-expressing in order to randomize the subject).

- Participants must have the result of tumor cell PD-L1 IHC testing from the Central Lab available (and HPV p-16 result if not available locally) in order to randomize into the study.
- Participant is assessed for study eligibility.
- All screening assessments and procedures must be performed prior to randomization.

Treatment Phase

- The treatment begins with the contact to the IVRS to randomize the patient.
- Treatment to begin within 3 days of randomization.

Arm A: Nivolumab + Ipilimumab Combo (1 Cycle = 6 Weeks):

- Nivolumab 3 mg/kg IV will be administered every 2 weeks (\pm 3 days) + Ipilimumab 1 mg/kg IV will be administered every 6 weeks (\pm 3 days).
- On the day of infusion, nivolumab is to be administered first. The second infusion will always be ipilimumab and will start at least 30 minutes after completion of the nivolumab infusion.
- Nivolumab 3 mg/kg Q2W and ipilimumab 1 mg/kg Q6W will be continued until the progression of disease, discontinuation due to toxicity, withdrawal of consent, or a maximum of 24 months from the first study treatment, or study closure (see [Section 3.5](#) for full list of treatment discontinuation reasons). Participants may discontinue only ipilimumab and continue treatment with nivolumab if certain circumstances are met (See [Section 4.5.6](#), Treatment Beyond Disease Progression (Arm A only).
- Treatment beyond initial investigator-assessed RECIST 1.1-defined progression is permitted for Arm A if the participant has investigator-assessed clinical benefit and is tolerating treatment.

Arm B: EXTREME regimen Arm (1 Cycle = 3 weeks):

- Cetuximab 400 mg/m² IV for the initial dose only, then 250 mg/m² weekly + cisplatin (100 mg/m²) or carboplatin (AUC of 5 mg per milliliter per minute) on Day 1 and fluorouracil (1000 mg/m² per day for 4 days) every 3 weeks for maximum of 6 cycles followed by maintenance cetuximab at 250 mg/m² weekly (or every 2 weeks, per local prescribing information) until disease progression or unacceptable toxicity; the choice of cisplatin or carboplatin is at the discretion of the investigator.
- Study assessments are to be collected as outlined in [Table 5.1-2](#)
- Upon completion of dosing, participants will enter the Follow-up Phase.

Follow-up Phase

The post-treatment follow-up begins when the decision to discontinue a participant from all treatment is made.

- Participants who discontinue treatment for reasons other than disease progression will continue to have tumor assessments (if clinically feasible) according to the schedule in [Table 5.1-3](#) until progression.

Participants will be followed for drug-related toxicities until these toxicities resolve, return to baseline or are deemed irreversible. All adverse events will be documented for a minimum of 100 days after the last dose of study medication.

After completion of the first 2 follow-up visits, participants will be followed every 3 months for survival. Survival Follow-up visits may be performed by phone contact or office visit. BMS may request that survival data be collected on all treated participants outside of the protocol-defined window. At that time of this request, each participant will be contacted to determine their survival status unless the participant had withdrawn consent for all contact.

3.2 Post Study Access to Therapy

At the conclusion of the study, participants who continue to demonstrate clinical benefit will be eligible to receive BMS supplied study drug for the maximum treatment duration as described in [Section 1.2.6](#). Study drug will be provided via an extension of the study, a rollover study requiring approval by responsible health authority and ethics committee or through another mechanism at the discretion of BMS. BMS reserves the right to terminate access to BMS supplied study drug if any of the following occur: a) the marketing application is rejected by responsible health authority; b) the study is terminated due to safety concerns; c) the participant can obtain medication from a government sponsored or private health program; or d) therapeutic alternatives become available in the local market.

3.3 Study Population

For entry into the study, the following criteria MUST be met:

3.3.1 Inclusion Criteria

1. Signed Written Informed Consent

- a) Participants must have signed and dated an IRB/IEC approved written informed consent form in accordance with regulatory and institutional guidelines. This must be obtained before the performance of any protocol related procedures that are not part of normal subject care.
- b) Participants must be willing and able to comply with scheduled visits, treatment schedule, and laboratory testing.

2. Target Population

- a) Histologically confirmed head and neck squamous cell carcinoma (SCCHN), from any of the following primary sites only: oral cavity, oropharynx, hypopharynx and larynx.
- b) Must have metastatic or recurrent disease that is not amenable to therapy with curative intent (surgery or radiation therapy with or without chemotherapy). Participants that refuse potentially curative salvage surgery for recurrent disease are ineligible.
- c) No prior treatment with systemic anti-cancer therapy for SCCHN, unless under all of the following conditions:
 - i) Prior chemotherapy was given as adjuvant or neoadjuvant chemotherapy, or part of multimodal (chemo, radiation) treatment for locally advanced disease
 - ii) These treatments must have been completed > 6 months prior to enrollment
 - iii) There is no evidence of disease progression for at least 6 months after completion of systemic treatment.
 - iv) Participants having progression after 2 cycles of induction chemotherapy are excluded.
- d) ECOG Performance Status of 0–1. (See [Appendix 1](#)).
- e) Measurable disease by CT or MRI per RECIST 1.1 criteria (see [Appendix 3](#)); radiographic tumor assessment performed within 28 days prior to first dose.
 - i) Target lesions may be located in a previously irradiated field if there is documented (radiographic) disease progression in that site after the completion of radiation therapy.
- f) Documentation of HPV p-16 status is required for SCCHN tumor of the oropharynx. See [Section 5.6.8](#) for additional guidance. Note: If results are not available, then a sample (tissue on microscopic slides, tissue block or a fresh tissue biopsy in formalin) should be sent to the central laboratory for analysis.
- g) Documentation of tumor cell PD-L1 status by IHC performed by the central lab prior to randomization.

Either a formalin-fixed, paraffin-embedded (FFPE) tissue block or unstained tumor tissue sections (archival or recent), with an associated pathology report, must be submitted for biomarker evaluation prior to randomization as described in [Section 5.6.3](#). Biopsy should be excisional, incisional, or core needle. Fine needle aspiration is insufficient. Biopsies of bone lesions that do not have a soft tissue component are unacceptable for submission.

- h) **As of Revised Protocol 02, this criterion has been altered and rewritten as criterion 2.1.** *Prior palliative radiotherapy must have been completed at least 8 weeks prior to randomization if radiotherapy was to the head and neck region and 4 weeks prior to randomization if radiotherapy was to other regions.*
- i) All toxicities attributed to prior systemic anti-cancer therapy or surgery other than alopecia and fatigue must have resolved or returned to baseline at least 2 weeks before randomization.
- j) Participants must have a life expectancy of at least 3 months. Any participants whose body weight decreased by > 10% between the screening visit and randomization must be excluded from the study.
- k) **As of Revised Protocol 02, this criterion has been removed because it is already part of criterion c.** *Participants having progression after 2 cycles of induction chemotherapy are excluded.*
- l) Prior radiotherapy must have been completed at least 2 weeks prior to randomization. All toxicities attributed to the radiotherapy must have resolved or returned to baseline prior to treatment.

3. Age and Reproductive Status

- a) Males and Females, ages ≥ 18 years of age
- b) Women of childbearing potential (WOCBP) must have a negative serum or urine pregnancy test (minimum sensitivity 25 IU/L or equivalent units of HCG) within 24 hours prior to the start of study drug.
- c) Women must not be breastfeeding
- d) WOCBP must agree to follow instructions for method(s) of contraception from the time of enrollment for the duration of treatment plus 5 half-lives of nivolumab (half-life up to 25 days) plus 30 days (duration of ovulatory cycle) for a total of 5 months post treatment completion (Arm A).
 - i. WOCBP must also agree to follow instructions for method(s) of contraception from the time of enrollment for the duration of treatment with chemotherapy plus 5-half-lives of chemotherapy plus 30 days (duration of ovulatory cycle) for a total of 30 days post-treatment completion or a duration specified by the local labels of the chemotherapy drugs received, whichever is longer (Arm B).

- e) Men who are sexually active with WOCBP must agree to follow instructions for method(s) of contraception for the duration of treatment with nivolumab plus 5 half-lives of nivolumab plus 90 days (duration of sperm turnover) for a total of 7 months post treatment completion (for participants treated in Arm A).
 - i. Men who are sexually active with WOCBP must agree to follow instructions for method(s) of contraception for the duration of treatment with chemotherapy plus 5 half-lives of chemotherapy plus 90 days (duration of sperm turnover) for a total of 90 days post-treatment completion or a duration specified by the local labels of the chemotherapy drugs received, whichever is longer (for participants treated in Arm B).
- f) Azoospermic males and WOCBP who are continuously not heterosexually active are exempt from contraceptive requirements. However they must still undergo pregnancy testing as described in these sections.

Investigators shall counsel WOCBP and male participants who are sexually active with WOCBP on the importance of pregnancy prevention and the implications of an unexpected pregnancy. Investigators shall advise WOCBP and male participants who are sexually active with WOCBP on the use of highly effective methods of contraception. Highly effective methods of contraception (see [Appendix 4](#)) which have a failure rate of < 1% when used consistently and correctly.

At a minimum, participants must agree to use one highly effective method of contraception as listed in Appendix 4.

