3.3.3 Women of Childbearing Potential

A woman of childbearing potential (WOCBP) is defined as any female who has experienced menarche and who has not undergone surgical sterilization (hysterectomy or bilateral oophorectomy) and is not postmenopausal. Menopause is defined as 12 months of amenorrhea in a woman over age 45 years in the absence of other biological or physiological causes. In addition, females under the age of 55 years must have a serum follicle stimulating hormone (FSH) level > 40 mIU/mL to confirm menopause.

Females treated with hormone replacement therapy (HRT) are likely to have artificially suppressed FSH levels and may require a washout period in order to obtain a physiologic FSH level. The duration of the washout period is a function of the type of HRT used. The duration of the washout period below are suggested guidelines and the investigators should use their judgment in checking serum FSH levels. If the serum FSH level is > 40 mIU/mL at any time during the washout period, the woman can be considered postmenopausal:

- 1 week minimum for vaginal hormonal products (rings, creams, gels)
- 4 week minimum for transdermal products
- 8 week minimum for oral products

Other parenteral products may require washout periods as long as 6 months. If the serum FSH level is > 40 mIU/mL at any time during the washout period, the woman can be considered postmenopausal.

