APPENDIX 4 WOMEN OF CHILDBEARING POTENTIAL DEFINITIONS AND METHODS OF CONTRACEPTION

DEFINITIONS

Woman of Childbearing Potential (WOCBP)

A woman is considered fertile following menarche and until becoming post-menopausal unless permanently sterile. Permanent sterilization methods include hysterectomy, bilateral salpingectomy, and bilateral oophorectomy.

Women in the following categories are not considered WOCBP

- Premenarchal
- Premenopausal female with 1 of the following:
 - Documented hysterectomy
 - Documented bilateral salpingectomy
 - Documented bilateral oophorectomy

Note: Documentation can come from the site personnel's review of the participant's medical records, medical examination, or medical history interview.

- Postmenopausal female
 - A postmenopausal state is defined as 12 months of amenorrhea in a woman over age 45 years in the absence of other biological or physiological causes. In addition, females under the age of 55 years must have a serum follicle stimulating hormone, (FSH) level > 40 mIU/mL to confirm menopause.

CONTRACEPTION GUIDANCE FOR FEMALE PARTICIPANTS OF CHILD BEARING POTENTIAL

One of the highly effective methods of contraception listed below is required during study duration and until the end of relevant systemic exposure, defined as 5 months after the end of study treatment.*

Highly Effective Contraceptive Methods That Are User Dependent

Failure rate of <1% per year when used consistently and correctly.^a

- | |
|--|
| 
• Combined (estrogen- and progestogen-containing) hormonal contraception associated with inhibition of ovulation and/or implantation (These methods of contraception cannot be used by WOCBP participants in studies where hormonal contraception is prohibited)^b
– oral (birth control pills)– intravaginal (vaginal birth control suppositories, rings, creams, gels)– transdermal |
|--|

 • Progestogen-only hormonal contraception associated with inhibition of ovulation^b 
 – oral – injectable

Highly Effective Methods That Are User Independent

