*** Local laws and regulations may require use of alternative and/or additional contraception methods.**

CONTRACEPTION GUIDANCE FOR MALE PARTICIPANTS WITH PARTNER(S) OF CHILD BEARING POTENTIAL.

Male participants with female partners of childbearing potential are eligible to participate if they agree to the following during the treatment and until the end of relevant systemic exposure.

- Inform any and all partner(s) of their participation in a clinical drug study and the need to comply with contraception instructions as directed by the investigator.
- Male participants are required to use a condom for study duration and until end of relevant systemic exposure defined as 7 months after the end of study treatment.
- Female partners of males participating in the study to consider use of effective methods of contraception until the end of relevant systemic exposure, defined as 7 months after the end of treatment in the male participant.
- Male participants with a pregnant or breastfeeding partner must agree to remain abstinent from penile vaginal intercourse or use a male condom during each episode of penile penetration during the treatment and until 7 months after the end of study treatment.
- Refrain from donating sperm for the duration of the study treatment and until 7 months after the end of study treatment.

COLLECTION OF PREGNANCY INFORMATION

Guidance for collection of Pregnancy Information and outcome of pregnancy on the Pregnancy Surveillance Form is provided in [Section 6.4](#).

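### Arm B post-treatment contraception: Section 3.3.1 and Appendix 4 state different periods, and the Arm B formula does not match its own total

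*Protocol*

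**What the plan says.** Section 3.3.1 sets the post-treatment period by arm and sex.

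- **Arm A, women (3.d):** the time on treatment, and then "plus 5 half-lives of nivolumab (half-life up to 25 days) plus 30 days (duration of ovulatory cycle"; the criterion gives the sum as 5 months.
- **Arm A, men (3.e):** the same half-life term plus 90 days, stated as 7 months.
- **Arm B, women (3.d.i):** treatment "plus 5-half-lives of chemotherapy plus 30 days (duration of ovulatory cycle) for a total of 30 days post-treatment completion".
- **Arm B, men (3.e.i):** five half-lives of chemotherapy plus 90 days, "for a total of 90 days post-treatment completion".

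Both Arm B criteria add that a longer local label duration takes precedence. For methods, Section 3.3.1 refers the reader to Appendix 4.

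Appendix 4 gives its own periods. Women use a highly effective method "until the end of relevant systemic exposure, defined as 5 months after the end of study treatment". Men must "use a condom for study duration and until end of relevant systemic exposure defined as 7 months after the end of study treatment", and the same 7 months applies to sperm donation. The male list is introduced as something participants must agree to in order to be eligible. Neither period is limited to an arm.

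On who counts as a woman of childbearing potential (WOCBP), Section 3.3.3 includes a woman past menarche "who has not undergone surgical sterilization (hysterectomy or bilateral oophorectomy) and is not postmenopausal". Appendix 4 also excludes a premenopausal woman with "Documented bilateral salpingectomy".

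**The concern.** The contraception periods are undertakings given at entry to limit embryo-fetal exposure. An investigator who applies criteria 3.d.i and 3.e.i to an Arm B participant and one who applies Appendix 4 would arrive at different periods, and nothing in the text says which governs. Section 3.3.2 closes by allowing no exceptions to the eligibility criteria, so a conflict between two statements of the same undertaking leaves a site unable to show that it complied with both unless it happens to use the longer period.

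The Arm B wording also conflicts with itself. It adds a half-life term to 30 or 90 days and then reports a total that leaves the term out. It speaks of chemotherapy, while Section 4.5.1.2 lets Arm B participants continue on cetuximab alone after six cycles. Whether cetuximab is covered by the formula or by the label clause is not stated.

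**Working it through.** **Inputs.** Nivolumab half-life up to 25 days, and the added 30 and 90 days (Section 3.3.1). Appendix 4 periods of 5 and 7 months. Conversion of 1 month = 30.4375 days (SAP Section 8). No half-life is given for any Arm B drug; call it h, in days.

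**Formula in the text.** Period = 5 × half-life + added days.

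**Step 1: check the formula on Arm A.**
- Women: 5 × 25 + 30 = 155 days; 155 / 30.4375 = 5.09 months (stated 5).
- Men: 5 × 25 + 90 = 215 days; 215 / 30.4375 = 7.06 months (stated 7).

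The stated figures are reproduced, rounded down by 155 − 152.2 = 2.8 days and 215 − 213.1 = 1.9 days.

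**Step 2: apply it to Arm B.**
- Women: 5h + 30 = 30 requires h = 0.
- Men: 5h + 90 = 90 requires h = 0.

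The stated totals therefore do not follow from the stated sum. The size of the discrepancy is 5h. The half-lives below are assumptions used only to show the range.

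| Assumed half-life | 5h (days) | Women, 5h + 30 | Men, 5h + 90 |
|---|---|---|---|
| 1 hour | 0.2 | 30.2 | 90.2 |
| 6 hours | 1.3 | 31.3 | 91.3 |
| 24 hours | 5 | 35 | 95 |
| 5 days | 25 | 55 | 115 |
| 7 days | 35 | 65 | 125 |

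**Step 3: compare Arm B in Section 3.3.1 with Appendix 4.**
- Women: 5 × 30.4375 = 152.2 days; 152.2 − 30 = 122 days.
- Men: 7 × 30.4375 = 213.1 days; 213.1 − 90 = 123 days.

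These are maximum gaps, because 30 and 90 days are minimums.

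**Step 4: what half-life would make the two places agree?** Women: (152.2 − 30) / 5 = 24.4 days. Men: (213.1 − 90) / 5 = 24.6 days. Both are close to the 25 days given for nivolumab. The Appendix 4 periods match the Arm A periods but carry no Arm A label.

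**Step 5: does Appendix 4 reach Arm B?** Its periods run from the end of study treatment. Table 4-1 and Section 4.1 list cetuximab, cisplatin, carboplatin and fluorouracil as study drugs and investigational products. On the protocol's own terms, Arm B participants are included.

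**Step 6: childbearing potential.** A premenopausal woman with bilateral salpingectomy and no hysterectomy or oophorectomy is a WOCBP under Section 3.3.3 and is not one under Appendix 4.

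**The case against.** The best defence is that the durations belong to the eligibility criteria and that Section 3.3.1 cites Appendix 4 for methods only, so the appendix merely lacks an arm label. The longer period also satisfies the shorter minimum, so the two can be met together. The second point is true, but it does not tell a site which period is required. The first would be stronger if Appendix 4 listed only methods. It states durations of its own, and for men it states them as conditions of eligibility.

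Four stronger readings are tempting, and the documents do not support them.

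- **That control participants get exactly 30 or 90 days.** The label clause makes these minimums. Label durations are not in the documents, so the actual gap may be smaller for some drugs or countries.
- **That the Arm B sum hides a material error.** With half-lives of 1 to 6 hours the excess is 0.2 to 1.3 days, less than the rounding accepted for Arm A. It becomes material only under an assumed half-life of days.
- **That cetuximab is left out.** Section 1.6 calls the EXTREME regimen chemotherapy, and Section 4.5.4.3 puts cetuximab rules under a chemotherapy heading. Section 8.1, describing the comparator of a cited first-line trial, names cetuximab separately from chemotherapy. The usage is mixed, so this is an ambiguity and not a demonstrated omission.
- **That all of roughly 465 control participants (930 / 2) are affected.** The documents do not count WOCBP or men with WOCBP partners, and criterion 3.f exempts some.

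What participants are actually told cannot be checked here either, since the consent form is not among the documents. The salpingectomy difference is minor: Section 3.3.3 is simply the broader definition.

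**Conclusion.** The contradiction between Section 3.3.1 and Appendix 4 holds on the current text. For Arm B, the written minimums of 30 days (women) and 90 days (men) sit against 5 and 7 months, a difference of up to about 122 and 123 days. This rests on reading study treatment to include the Arm B drugs, which the protocol's own drug tables support, and on the SAP's month length. It shrinks wherever a local label exceeds the minimum.

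The Arm B formula and its total are inconsistent as written, but the size of that slip is undetermined, because no Arm B half-life is stated and the scope of the word chemotherapy is unclear. The two definitions of childbearing potential differ for bilateral salpingectomy. None of this touches an endpoint, an analysis population or the sample size. It is a safety-wording inconsistency that should be corrected.

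**What to change.** The sponsor should reconcile criteria 3.d.i and 3.e.i of Section 3.3.1 with the female and male guidance in Appendix 4, so that each arm and sex has one stated period and both places give it. In the Arm B criteria, the formula, the total and the drugs covered should be made to agree, with an explicit statement of whether cetuximab is included. Section 3.3.3 and Appendix 4 should carry one WOCBP definition. Which period and which definition apply is for the sponsor to decide; no choice is proposed here.

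The cost is protocol wording, with matching consent wording where it repeats these periods. Sample size, data collection for the efficacy endpoints and the analyses are unchanged.
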